**Notes:**

- Since SF level may be impacted by the presence of infection, it must additionally be verified that the child has had no signs of infection in the previous 7 days, including the day of the visit, and that the level of CRP is no greater than 20% higher than the normal range for the patient's age. . . If there are signs of infection and/or the CRP level is above this threshold, an SF level  $\geq 1000 \mu\text{g/L}$  must be checked again a minimum of a week later. (If an investigator has valid reason to believe that an SF level  $\geq 1000 \mu\text{g/L}$  may be attributable to infection even if this is not indicated by the CRP result, SF may be rechecked once more a minimum of one week later.)
- If a transfusion is scheduled on the day of the visit, the blood samples for serum ferritin, LPI, and TSAT must be collected before the transfusion is performed.
- Collect a urine specimen for urinalysis
- Perform a physical examination (to be completed by the investigator or a qualified delegate)
- Measure vital signs (heart rate, blood pressure, and body temperature)
- Measure weight and height/length
- Review and update transfusion history
- Ask about any adverse events that have occurred and concomitant medications that have been taken since the last site visit
- Additionally review the diary card for information on adverse events and use of concomitant medications, and file the diary card with the source documents
- Collect study medication containers, and check them to calculate treatment compliance
- Administer the final dose of study medication, ensuring that this is done at approximately the same time as at baseline, and note the exact time at which it is given
- Collect a blood sample for the assessment of prolactin at 1.5 hours ( $\pm 5 \text{ min}$ ) post-dose

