### **7.1.1 Serum Ferritin**

Ferritin is a protein that stores iron in a non-toxic form, transports it to areas where it is required, and releases it in a controlled manner, thereby acting as a buffer against iron deficiency and iron overload. It is mainly found in tissues, but small amounts are secreted into the serum, where it can serve as an indirect but easily measurable marker of the total amount of iron stored in the body. (Drawbacks of using it as a marker include lack of specificity, as disorders other than iron overload can cause large amounts of ferritin to be released into the circulation, and inter-patient variability.) Levels of serum ferritin above 1000 ng/mL are often considered to be associated with iron toxicity. In young children who have only recently begun an RBC transfusion regimen, it takes some time for this level to be reached, but in the absence of chelation it inevitably is reached.

Serum ferritin will be measured at each visit, and the time to reach a level  $\geq 1000 \mu\text{g/L}$  will be compared between the treatment arms.

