### 9.2 Determination of Sample Size and Study Power

The sample size for this study is 64 patients, randomized in a 1:1 ratio to the two arms. With this number of patients, there will be over 90% power to detect a statistically significant difference ( $\alpha = 0.05$ ) between the two treatment groups in the percentage of patients who have a serum ferritin level  $< 1000 \mu\text{g/L}$  at Month 12 if the deferiprone arm and the placebo arm have an expected incidence of 70% and 20%, respectively.

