## **5. Statistical Analysis**

A two-sided p-value of 0.05 will be used as the significance level for the determination of statistical significance in all statistical tests.

All statistical analyses of efficacy and safety data will be performed using SAS (version 9.4 or higher) on the Windows operating system.

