### **5.2.2 Secondary Efficacy Endpoints**

The secondary efficacy endpoints are:

- The percentage of patients whose serum ferritin level is still less than 1000  $\mu\text{g}/\text{L}$  at each visit
- The percentage of patients whose LPI value is still less than 0.6  $\mu\text{M}$  at each visit
- The percentage of patients whose TSAT value is still less than 60% at each visit
- Time to reach a serum ferritin level  $\geq 1000 \mu\text{g}/\text{L}$  (Note: a patient is to be withdrawn from the study only if the repeated serum ferritin level is  $\geq 1000 \mu\text{g}/\text{L}$ .)
- Time to reach an LPI value  $\geq 0.6 \mu\text{M}$
- Time to reach a TSAT value  $\geq 60\%$

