## 5.6 Analysis of Efficacy

The percentage of patients who have not reached levels of  $LPI \geq 0.6 \mu M$ ,  $TSAT \geq 60\%$ , or  $SF \geq 1000 \mu g/L$  will be compared between the two treatment groups at each monthly time point as well as at the end of study, using the Fisher's exact test. (Note: the repeated SF value will be used to determine this for those patients whose SF is  $\geq 1000 \mu g/L$ .)

The effect of baseline value on each of the 3 efficacy endpoints will be examined in a covariate analysis. As an example for serum ferritin, the following SAS code of MIXED procedure will be used to produce the differences in Least Squares (LS) Mean of change in serum ferritin at Months 1, 2, 3, 4, 5, 6, 7, 8, 9, 10, 11, and 12 between deferiprone and placebo groups and the corresponding 95% confidence intervals.

```

proc mixed data=sf;
  class patient base_sf treat month;
  model sf_change = base_sf treat month treat*month /
    noint solution ddfm=kr;
  repeated month / Patient=patient(treat) type=ar(1);
  lsmeans treat*month;
  estimate 'Deferiprone - Placebo at Month 1'
    treat 1 -1
    treat*month  1 0 0 0 0 0 0 0 0 0 0 0
                 -1 0 0 0 0 0 0 0 0 0 0 0 / cl alpha=0.05;
  estimate 'Deferiprone - Placebo at Month 2'
    treat 1 -1
    treat*month  0 1 0 0 0 0 0 0 0 0 0 0
                 0 -1 0 0 0 0 0 0 0 0 0 0 / cl alpha=0.05;
  estimate 'Deferiprone - Placebo at Month 3'
    treat 1 -1
    treat*month  0 0 1 0 0 0 0 0 0 0 0 0
                 0 0 -1 0 0 0 0 0 0 0 0 0 / cl alpha=0.05;
  estimate 'Deferiprone - Placebo at Month 4'
    treat 1 -1
    treat*month  0 0 0 1 0 0 0 0 0 0 0 0
                 0 0 0 -1 0 0 0 0 0 0 0 0 / cl alpha=0.05;
  estimate 'Deferiprone - Placebo at Month 5'
    treat 1 -1
    treat*month  0 0 0 0 1 0 0 0 0 0 0 0
                 0 0 0 0 -1 0 0 0 0 0 0 0 / cl alpha=0.05;
  estimate 'Deferiprone - Placebo at Month 6'
    treat 1 -1
    treat*month  0 0 0 0 0 1 0 0 0 0 0 0
                 0 0 0 0 0 -1 0 0 0 0 0 0 / cl alpha=0.05;

```

```

estimate 'Deferiprone - Placebo at Month 7'
  treat 1 -1
  treat*month  0 0 0 0 0 0  1 0 0 0 0 0
                0 0 0 0 0 0 -1 0 0 0 0 0/ cl alpha=0.05;
estimate 'Deferiprone - Placebo at Month 8'
  treat 1 -1
  treat*month  0 0 0 0 0 0  1 0 0 0 0
                0 0 0 0 0 0 0 -1 0 0 0 0/ cl alpha=0.05;
estimate 'Deferiprone - Placebo at Month 9'
  treat 1 -1
  treat*month  0 0 0 0 0 0 0 0  1 0 0 0
                0 0 0 0 0 0 0 0 -1 0 0 0/ cl alpha=0.05;

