estimate 'Deferiprone - Placebo at Month 10'
  treat 1 -1
  treat*month  0 0 0 0 0 0 0 0 0  1 0 0
                0 0 0 0 0 0 0 0 0 -1 0 0/ cl alpha=0.05;
estimate 'Deferiprone - Placebo at Month 11'
  treat 1 -1
  treat*month  0 0 0 0 0 0 0 0 0  1 0
                0 0 0 0 0 0 0 0 0 0 -1 0/ cl alpha=0.05;
estimate 'Deferiprone - Placebo at Month 12'
  treat 1 -1
  treat*month  0 0 0 0 0 0 0 0 0  1
                0 0 0 0 0 0 0 0 0 0 -1/ cl alpha=0.05;
run;

```

A Kaplan-Meier survival curve for the time to reach a serum ferritin level  $\geq 1000 \mu\text{g/L}$ , an LPI value  $\geq 0.6 \mu\text{M}$ , or a TSAT value  $\geq 60\%$  will be generated for the two treatment groups. Log-rank test will be used for comparing the two survival curves for each of the 3 efficacy endpoints.

As an example, for serum ferritin, the following SAS code of LIFETEST procedure will be used to compare the two survival curves. A variable status is the censoring indicator. A status of 1 indicates an event time when a serum ferritin level reaches  $\geq 1000 \mu\text{g/L}$  and a status of 0 indicates the event of serum ferritin level  $\geq 1000 \mu\text{g/L}$  has not occurred by the end of the study.

```

proc lifetest data=sf method=km plot=(s) graphics;
  time month*status(0);
  strata treat;
run;

```

Trend analysis over time for LPI, TSAT, and SF measures will be performed to compare the rate of change per month in these measures between the two treatment groups. As an example, for serum ferritin, the following SAS code of MIXED procedure will be used to compare the two slopes between the two treatment groups:

```
proc mixed data=sf;
  class treat patient;
  model sf = treat month treat*month / noint solution;
  repeated / type=ar(1) Patient=patient(treat);
  estimate 'Slope for deferiprone' month 1 treat*month 1 0;
  estimate 'Slope for placebo' month 1 treat*month 0 1;
  estimate 'Slope for deferiprone minus placebo' treat*month 1 -1;
run;
```

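### The serum ferritin event in the SAP 5.6 time-to-event analysis needs no confirmation, unlike withdrawal and the percentage analyses, and an unrepeated first high value at Month 12 has no rule

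*SAP*

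**What the plan says.** Four places handle the 1000 µg/L threshold.

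- **Withdrawal.** Protocol 3.1 and 4.5 require SF ≥1000 at two consecutive visits, with no infection signs in the previous 7 days and CRP no more than 20% above the normal range for age.
- **Percentage analyses.** In SAP 5.6 the Fisher comparisons, at each month and at end of study, carry a note that "the repeated SF value will be used to determine this for those patients whose SF is" 1000 or above.
- **Time to event.** For the log-rank comparison, SAP 5.6 says "A status of 1 indicates an event time when a serum ferritin level reaches" 1000 or above. It mentions no repeat and no infection or CRP condition, and does not say which date counts if there are two values. The note beside this endpoint in SAP 5.2.2 concerns exit only: "a patient is to be withdrawn from the study only if the repeated serum ferritin level is" at or above the threshold.
- **Month 12.** The recheck in Protocol 5.1 is conditional: "If there are signs of infection and/or the CRP level is above this threshold, an SF level" of 1000 or more is to be measured again at least a week later. Otherwise a recheck is left to the investigator's judgment.

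Protocol 7.1.1 gives the reason for caution: "disorders other than iron overload can cause large amounts of ferritin to be released into the circulation".

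**The concern.** The protocol treats a single high ferritin as unreliable and will not withdraw a child on it. The Kaplan-Meier definition does not carry that caution over. A programmer coding from SAP 5.6 would set the event at the first value ≥1000. Take a child with one high value at Month 3 who is below 1000 at every later visit: an event at Month 3 in the log-rank test, and a success in the primary analysis. The main supporting endpoint would then partly measure ferritin noise instead of iron loading.

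Month 12 raises a different problem. At earlier visits a first high value is followed by another visit. At Month 12 it is not, and the recheck is required only with infection signs or raised CRP. The Fisher rule then depends on a repeated value that may not exist, at the time point that decides the primary endpoint. The choice would fall to whoever programs the analysis.

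**Working it through.** **1. The plan's own power figure.** Inputs: 32 per arm (Protocol 4.1); "A two-sided p-value of 0.05 will be used as the significance level" (SAP 5); "there will be over 90% power to detect a statistically significant difference" "if the deferiprone arm and the placebo arm have an expected incidence of 70% and 20%, respectively" (Protocol 9.2).

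Pooled normal approximation, with mean rate (0.70 + 0.20)/2 = 0.45:

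- z = [0.50·√32 − 1.96·√(2·0.45·0.55)] / √(0.70·0.30 + 0.20·0.80)
- = (2.828 − 1.379)/0.608 = 2.38, so power is 99.1%.

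Exact Fisher power, enumerating Binomial(32, 0.70) against Binomial(32, 0.20), is 98.3%. Both agree with the stated figure.

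**2. Effect of the event definition.** The documents give no within-child ferritin variability. I therefore assume a chance q that a child truly below 1000 shows an isolated value ≥1000 at a visit, independently over 12 monthly visits, and vary q from 1% to 10%.

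- Single-value rule: P(false event) = 1 − (1 − q)^12. For q = 1%, 1 − 0.99^12 = 11.4%.
- Two-consecutive rule: let a be the probability of no run so far with the last value low, and b the same with the last value high. Start at a = 1, b = 0. At each visit, add b·q to the false-event probability, then set a to (a + b)(1 − q) and b to (old a)·q.

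Expected children truly below 1000 at the planned rates: 32 × 0.70 = 22.4 on deferiprone and 32 × 0.20 = 6.4 on placebo. Multiplying by the difference between the two rules gives the number who are events only because confirmation is not required.

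| q (assumed) | Single value | Two consecutive | Extra false events, deferiprone | Extra false events, placebo |
|---|---|---|---|---|
| 1% | 11.4% | 0.1% | 2.5 | 0.7 |
| 2% | 21.5% | 0.4% | 4.7 | 1.4 |
| 5% | 46.0% | 2.6% | 9.7 | 2.8 |
| 10% | 71.8% | 9.7% | 13.9 | 4.0 |

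The 12 visits include Month 12. Counting only the 11 visits before it, the single-value figures are 1 − 0.99^11 = 10.5% at q = 1% and 1 − 0.90^11 = 68.6% at q = 10%, so the picture is the same.

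Independence is a simplification. If a child's high values cluster, two in a row become more likely and the gap between the rules narrows.

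**3. Effect on the primary endpoint.** As the adverse case, count every isolated high Month 12 reading as a failure. The rates become 0.70(1 − q) and 0.20(1 − q):

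| q (assumed) | Rates | Exact Fisher power |
|---|---|---|
| 0 | 70.0% v 20.0% | 98.3% |
| 1% | 69.3% v 19.8% | 98.1% |
| 2% | 68.6% v 19.6% | 97.8% |
| 5% | 66.5% v 19.0% | about 97% |
| 10% | 63.0% v 18.0% | 95.3% |

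The Month 12 gap leaves the primary endpoint incompletely defined. It does not threaten the planned power.

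**The case against.** The strongest reply is that the Kaplan-Meier text is silent on confirmation and does not rule it out. The repeat note stands in the same section, and another note stands beside the endpoint itself. That is fair as to intent. But the first note belongs to the Fisher paragraph and the second speaks only of withdrawal, so neither changes the status variable as written.

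It can also be said that infection-driven rises are largely caught. CRP is drawn at the monthly visits, a high value with infection signs or raised CRP must be rechecked, and the investigator may recheck in other cases. This would lower q, but the event definition does not refer to that recheck. It also leaves fluctuation without infection.

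Time to first crossing and status at Month 12 are different quantities and may properly differ. The fault is that the threshold is reached under different rules in the two analyses, not that their results could disagree.

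Three stronger readings are tempting and are not supported:

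- **That an unrepeated Month 12 value is a failure.** The SAP does not say so; the case is undefined. Before Month 12, the repeated-value note means that isolated rises do not become failures in the percentage analyses.
- **That the burden falls mostly on deferiprone.** The earlier trial in Protocol 1.3 had most deferiprone crossings at 12 months. However, it used a fixed 50 mg/kg/day, and all its deferiprone patients had crossed by then, which does not fit the 70% assumed here. A simulation calibrated to 70% v 20% put unrepeated Month 12 crossings at 8.7–11.1% on deferiprone and 9.2–11.4% on placebo. It assumed linear rise, baseline SF uniform on 200–600, slope SD 20 per month and CV 10–25%; the slope SD and CV are not in the documents.
- **That the primary test loses material power.** At the protocol's own rates it does not.

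**Conclusion.** The point stands as an inconsistency of definition and a gap, and should be corrected. As written, the time-to-event analysis counts an SF event without the confirmation that withdrawal and the percentage analyses rely on. The same child can be an event there and a primary success.

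The size rests wholly on the assumed q and on independence between visits. Even at q = 1%, about one in nine children truly below 1000 would be a false event, and confirmation nearly removes this. At q = 10% the single-value curve would be dominated by false events.

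The text defects do not depend on q. The event definition omits the repeat, *repeated value* could mean a recheck after a week or the next monthly visit, and a first, infection-free SF ≥1000 at Month 12 has no stated classification.

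**What to change.** These are changes to SAP text only, made before unblinding.

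1. In SAP 5.6, set status to 1 only when SF ≥1000 is confirmed by the repeated value under the protocol's infection and CRP rule, with the event time at the first of the two values.
2. Define *repeated value* once, and use that definition in both the Kaplan-Meier and the Fisher analyses.
3. For a first SF ≥1000 at Month 12, or at a child's last visit, with no repeat: count the threshold as reached in both analyses, and report a sensitivity analysis with the opposite classification.
4. If wanted, keep time to first single value as a supportive analysis, labelled as such.
5. Reconcile the Month 12 notes in Protocol 5.1, the note in SAP 5.2.2, and the Fisher and Kaplan-Meier paragraphs of SAP 5.6.

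The cost is a few sentences, one line of derivation code and one extra sensitivity table. Sample size and visit procedures do not change. A routine extra Month 12 sample is not needed. It would retest only high values, so it could move children only towards success; it could fall after the final dose, which is given at that visit; and it would add a procedure.

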## 5.7 Analysis of Safety

Descriptive statistics (mean, standard deviation, minimum, and maximum) will be produced for continuous variables, and frequency tables will be produced for discrete variables by treatment group. Summaries of adverse events and serious adverse events will be produced by treatment group. Shift tables will be generated for comparing the screening/baseline values and end of study values of the relevant measures.

The following safety data will be summarized by treatment group:

- Adverse events (AEs), adverse drug reactions (ADRs), serious adverse events (SAEs), and serious adverse drug reactions (SADRs)
- Number of discontinuations due to AEs
- Hematology assessments
- Biochemistry assessments
- Urinalysis
- Vital signs
- Prior and concomitant medications

Prolactin is measured at baseline and Month 12. The change in prolactin level from baseline to Month 12 will be compared between the two treatment groups using an ANCOVA model with baseline value as a covariate and treatment as the main factor.

### 5.7.1 AEs and SAEs

Adverse events (AEs) are coded using MedDRA version 23.0 or higher. In counting the number of patients who experienced each AE, any patients who experienced the same AE multiple times will be counted only once for the corresponding preferred term (PT). Similarly, any patients who experienced multiple AEs within the same system organ class (SOC) will be counted only once for that SOC. AEs will be tabulated alphabetically by SOC; and within each SOC, the PTs will be presented alphabetically. In tables that present the incidence of AEs by severity, seriousness, and relation to study

medication, any patients with multiple events coded to a given PT or SOC will be counted only once for that PT or SOC according to the most severe event, the most serious event, or the event with the closest relationship to study medication.

AEs will be summarized for the total number of AEs, the total number and percent of patients who experienced at least one AE, and the total number and percent of patients who experienced an AE within each SOC (and each PT within an SOC). A p-value comparing the percentages of each AE among treatment groups will be calculated by using Fisher's exact test.

The incidences of AEs, SAEs, adverse drug reactions (ADRs), and serious ADRs (SADRs) will be tabulated by treatment group. The relationship to study medication for AEs will be tabulated by treatment group.

A listing of SAEs and a listing of withdrawals due to AEs with time to withdrawal will be produced. Any deaths will be listed separately and discussed in narratives.

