Patients will remain in the study for 12 months or until their SF level is found to be  $\geq 1000 \mu\text{g/L}$  at 2 consecutive visits, whichever comes first. Since SF level may be impacted by the presence of infection, it must additionally be verified that the child has had no signs of infection in the previous 7 days, including the day of the visit, and that the level of C-reactive protein (CRP) is no greater than 20% higher than the normal range for the patient's age. If there are signs of infection and/or the CRP level is above this threshold, the SF level must be checked again a minimum of one week later. (Note: If an investigator has valid reason to believe that an SF level  $\geq 1000 \mu\text{g/L}$  may be attributable to infection even if this is not indicated by the CRP result, SF may be rechecked once more a minimum of one week later.)

Patients whose SF levels are still under  $1000 \mu\text{g/L}$  at 12 months will be offered participation in an extension study, LA55-EXT, in which they will continue to receive their assigned study product for up to 2 more years. Those who are terminated early will not be eligible to enroll in the extension study.

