## 4 STUDY POPULATION

### 4.1 Number of Patients

A planned total of 64 patients will be enrolled in the study, 32 in each arm.

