#### **5.7.2 Number of discontinuations due to AEs**

The percent of patients who have been withdrawn for the study due to AEs will be compared between the two treatment groups using Fisher's exact test.

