## **14.3 Safety analyses**

### **14.3.1 Adverse events**

Table 14.3.1.1 Overall summary of adverse events

Table 14.3.1.2 Adverse events

Table 14.3.1.3 Most common Adverse Events  $\geq 5$  percent

Table 14.3.1.4 Adverse events with the maximum severity/intensity

Table 14.3.1.5 Adverse drug reactions

Table 14.3.1.6 Most common Adverse drug reactions  $\geq 5$  percent

Table 14.3.1.7 Adverse drug reaction with the maximum severity/intensity

Table 14.3.1.8 Serious adverse events

Table 14.3.1.9 Serious adverse events with the maximum severity/intensity

Table 14.3.1.10 Serious adverse drug reactions

Table 14.3.1.11 Serious adverse drug reactions with the maximum severity/intensity

Table 14.3.1.12 Adverse events by relatedness to study medication

Table 14.3.1.13 Adverse events – event count and rate

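### Adverse-event percentages are tested without regard to time at risk, although the ferritin exit rule is expected to shorten placebo follow-up, so common events spread over follow-up lean against deferiprone

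*SAP*

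**What the plan says.** **Tests.** Under SAP 5.7.1 a child counts at most once per preferred term and once per system organ class, whenever the event occurs and however long the child was followed. Then: "A p-value comparing the percentages of each AE among treatment groups will be calculated by using Fisher's exact test". In SAP 5.7.2 the percentages withdrawn because of AEs "will be compared between the two treatment groups using Fisher's exact test". The shells for ALT and AST above 2, 3 and 5 times the upper limit of normal also use Fisher's test on the share of children affected at any time in the study. SAP section 5 sets the level: "A two-sided p-value of 0.05 will be used as the significance level for the determination of statistical significance in all statistical tests".

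**Follow-up.** Protocol 3.1: "Patients will remain in the study for 12 months or until their SF level is found to be" at or above 1000 µg/L at two consecutive visits, whichever comes first. Protocol 4.5 makes that withdrawal compulsory, and 4.5.1 rules out replacement. Protocol 9.2 expects 70% of deferiprone and 20% of placebo children to be below 1000 µg/L at Month 12.

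**Exposure.** The SAP does not ignore it. The shell of Table 14.3.1.2 carries patient-years in its header, Tables 14.4.4 and 14.4.5 give exposure by arm, and Table 14.3.1.13 ("event count and rate") gives events per 100 patient-years. That last shell counts events, with no interval and no test. SAP 5.3 lists time to onset as an AE endpoint, but 5.7.1 gives it no method.

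**The concern.** Fisher's test on the share of children with an event treats every child as observed for the same time. Here the length of observation is an outcome of treatment: the better deferiprone holds ferritin down, the longer its children stay and the more time they have to record an ordinary childhood illness or a laboratory excursion. An AE hazard that is identical in the two arms then produces a higher expected percentage on deferiprone.

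Safety and tolerability are the trial's secondary objective, and the AE tables will print a p-value for every term. Some of those p-values could suggest harm when all that happened is that the drug delayed exit.

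**Working it through.** **Inputs from the documents.** "A planned total of 64 patients will be enrolled in the study, 32 in each arm"; two-sided 0.05; 70% v 20% below 1000 µg/L at Month 12; ferritin exit possible only from Month 2 (Protocol 5.1, early termination visit). In the earlier study described in Protocol 1.3, all unchelated children crossed at about 6 months, while 10% of deferiprone children had crossed by 9 months and the rest at 12.

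**Assumptions, not in the documents.** A constant AE hazard, equal in both arms, and the shape of the crossing times between baseline and Month 12.

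**The plan's own figure.** Protocol 9.2 says "there will be over 90% power to detect a statistically significant difference". Full enumeration of the two-sided Fisher test at 32 per arm, 70% v 20%, gives 98.3%, so the statement is met.

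**Exponential exits matching 70%/20%.** With S the share remaining at Month 12, the exit rate is λ = −ln(S)/12:
- Deferiprone: λ = 0.0297 per month, mean follow-up (1 − 0.7)/0.0297 = 10.1 months.
- Placebo: λ = 0.1341 per month, mean follow-up (1 − 0.2)/0.1341 = 6.0 months.

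With AE hazard r per month, the expected share with an event is r/(λ + r) × (1 − exp(−12(λ + r))). At r = 0.05:
- Deferiprone: 0.627 × 0.616 = 38.6%.
- Placebo: 0.272 × 0.890 = 24.2%.

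The exact Fisher test at 32 per arm then rejects in 17.0% of trials, practically always against deferiprone.

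**Other exit patterns, still 70%/20%, r = 0.05 per month (0.6 per year):**

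| Exits | Mean months, deferiprone v placebo | AE %, deferiprone v placebo | Fisher rejects |
|---|---|---|---|
| Exponential | 10.1 v 6.0 | 38.6 v 24.2 | 17.0% |
| Exponential, plus 1-month confirmation lag and 30 days of AE collection | 11.4 v 7.8 | 42.7 v 30.8 | 11.4% |
| Uniform, Months 2 to 12 | 10.5 v 8.0 | 40.2 v 32.1 | 6.7% |
| All in Months 10 to 12 | 11.7 v 11.2 | 44.3 v 42.8 | 3.3% |

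**Fixed follow-up, share = 1 − exp(−h·t):**

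| Months | Hazard per year | AE % | Fisher rejects |
|---|---|---|---|
| 12 v 7 (earlier study's timing, read with a month for confirmation) | 1 | 63.2 v 44.2 | 27.1% |
| 12 v 7 | 0.5 | 39.3 v 25.3 | 16.0% |
| 11.46 v 9.42 (a milder assumed split) | 1 | 61.5 v 54.4 | 6.0% |
| 11.46 v 9.42 | 0.5 | 38.0 v 32.5 | 4.6% |
| 12 v 7 | 0.12 | 11.3 v 6.8 | 2.4% |
| 11.46 v 9.42 | 0.12 | 10.8 v 9.0 | 1.3% |

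With equal follow-up, Fisher's test at 32 per arm rejects in about 3% of trials at hazards of 0.5 to 1 per year.

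**Would a simple rate repair it?** Suppose 30% of both arms have an event at Month 1 and none later. Months at risk per child are 0.3 × 1 + 0.7 × 12 = 8.7 on deferiprone and 0.3 × 1 + 0.7 × 7 = 5.2 on placebo. The first-event rate ratio is 5.2/8.7 = 0.60, or 0.83 with 11.46 v 9.42 months. It should be 1. Crude percentages are right in this case, because no ferritin exit precedes Month 2.

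**The case against.** The strongest reply has four parts.

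- **The size is assumed.** The documents do not say when children cross. The 12 v 7 month case borrows from a study in which every untreated child crossed, whereas this protocol expects 20% of placebo children not to. If crossings are late, the bias is under 2 percentage points. With the milder split, rejection stays between 4.6% and 6.0%. This stands, and it is why a range is given.
- **Individual terms are rarer than the hazards used.** No reaction in Protocol Table 1.1 exceeds 11.2%; neutropenia is 6.3% and increased ALT 7.6%. Those are drug reactions over an unstated exposure, so they do not bound all AEs. Still, at about 11% over 12 months rejection does not exceed 2.4%. The problem therefore concerns common background events, broad organ classes and the any-AE row. For rare terms the percentages lean the same way, but the p-value seldom crosses 0.05.
- **Some harms come early.** Protocol 3.3 expects gastrointestinal events when the drug is first introduced. Events in the first two months are hardly touched by ferritin exits. This also stands.
- **Exposure is partly handled.** Table 14.3.1.13 gives rates, and Protocol 7.2.1.2 collects AEs to 30 days after the last dose, which narrows the relative gap. Adding a month to both arms (13 v 8) still gives 23% rejection at 1 event per year. The rate table can be driven by repeat events in one child and leaves the tested comparison unadjusted.

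Two stronger readings are tempting. A reader might infer that Fisher's test is the only inferential safety comparison. It is not: the SAP also tests prolactin, height, weight and Z-scores by ANCOVA, time to withdrawal by log-rank, vital signs and laboratory values by t-test, and shifts by McNemar-Bowker. A reader might also infer material bias whenever the drug works. The late-exit case shows that this does not follow, and early exits for AEs on deferiprone would narrow the gap further.

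**Conclusion.** The concern holds for the comparison of AE incidence, including AE withdrawals and ALT/AST elevations. Given equal risk per unit time, the planned comparison of percentages leans against deferiprone for common events spread over follow-up, because the exit rule together with the plan's own 70%/20% expectation implies shorter placebo observation.

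The direction follows from the documents; the size does not. It ranges from nothing of consequence to a false-signal rate several times that under equal follow-up, depending on crossing times and on how common the event is. The exponential case marks the upper end of the patterns fitted to 70%/20%, since it lets exits begin at once. All figures assume a constant hazard equal in both arms, and exit unrelated to AE risk within an arm.

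**What to change.** For any AE, organ classes, preferred terms in at least 5% of children, neutropenia, ALT/AST elevations and AE withdrawals:

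1. **Main comparison:** time to first event, by Kaplan-Meier or cumulative incidence, with a log-rank test and a hazard ratio with 95% CI. Censor at study exit plus one stated post-dose window. This also supplies the missing method for the time-to-onset endpoint. State the assumption that exit is unrelated to AE risk within arm.
2. **Supportive only:** children with a first event per 100 patient-years with 95% CI. It assumes a constant hazard and understates early harm on the longer-followed arm, so it should not lead.
3. **Descriptive:** keep crude percentages, without p-values. Keep Table 14.3.1.13 as planned.
4. **Window:** reconcile the protocol synopsis, which collects AEs to Month 12 or early termination, with Protocol 7.2.1.2, which collects them to 30 days after the last dose. The SAP should then name the window that it analyses.

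The cost is SAP wording and a few table columns before database lock. The dates are already collected. Estimates for terms with few events will be imprecise, as they are under the present plan.
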